5.2 Study Drug

Study drug (Macimorelin) will be provided at no cost by Æterna Zentaris (AEZS). The Pharmaceutical Development group from AEZS has analyzed the stability of macimorelin in Powerade® for 7 days at both room temperature (25°C) and at 2-8°C. Data indicate that if stored refrigerated (2-8°C), the solution is stable over 7 days whereas at room temperature (25°C) it should not be stored longer than 3 days. Due to those results, macimorelin mixed in Powerade® and Powerade® alone will be prepared in individual doses by the MEDVAMC research pharmacy. Patients will receive macimorelin 1 mg/kg and matching placebo (Powerade®) according to the protocol as stated above in the 'study design' section. The study staff (PI, pharmacist, or authorized study coordinator) will dispense the product to the patients. On day 1 and 7, patients will be dosed at the clinical research center by the coordinator. From days 2 through 6, patients will self-administer the drug or placebo at home. Patients will be instructed to keep these doses in the refrigerator at 2-8°C and to drink them while fasting at least 1 hour before breakfast.

5.3 Blinding

The allocation schedule will be stored securely; no member of the investigational team involved in generation or review of the study database will be allowed to see the allocation schedule or data that may otherwise unblind treatment allocations. Two sealed envelopes will be kept for each patient. One will be kept in the Research Pharmacy and the other in the patient's file in case a patient needs to be unblinded. Unblinding should be avoided to the extent possible. Unblinding should only occur in emergencies for which knowledge of the treatment allocation will affect patient care decision-making. Formal unblinding of the study will occur after the database is locked or if requested by the DMC.

5.4 Drug Inventory and Disposition

An exact inventory of all study drug(s), including placebo, will be maintained at the investigational site. The study drug(s) will be stored in a locked storage area under environmental conditions appropriate for the product(s). All study drug(s) will be accounted for. Study drug(s) will only be shipped or destroyed upon written authorization from AEZS.

5.5 Screening Visit

- Screening evaluations will be performed within three weeks prior to the baseline visit and may occur on different days. Informed consent must be obtained prior to any screening procedures.
- Informed consent will be scanned and entered into our electronic medical records (CPRS) as per current VA guidelines.
- Following signature of informed consent, participants will be given a study ID using the format: [protocol#].[enrollment#]
- After signing the informed consent and review of inclusion and exclusion criteria, a complete history and physical exam (H&P) will be performed. Special emphasis will be placed on evaluation for any signs of pedal edema, pleural effusions, and ascites. Body weight will be obtained on a calibrated scale dedicated for this study. Patients will remove shoes, belts, wallets, keys, and cell phones. Underwear and a gown will be worn.
- A fasting blood sample (30 mL) will be obtained to measure safety labs including a complete blood count with differential (CBC with Differential), and comprehensive metabolic panel, and a UA (including hCG for females).
- An ECG also will be performed.
- Instructions and training for the proper use of the food diary will be given during the screening visit. Patients meeting the I/E criteria will be provided a 3-day food diary to assess food intake 3 days prior to their baseline visit.

- Selection of breakfast menu options: The patient will be asked to indicate his/her food preferences from several breakfast menu options for the test meal to be served at screening and again at the week 1 visit. The identical meal options will be provided on both days. A surplus of food will be provided so that availability of food does not limit caloric consumption.
- After informed consent but before the test meal is given, patients' brains will be imaged in a Phillips 3T scanner. Before starting the experiment, an investigator or trained technician will give the patient instructions on the safety of the MRI scan. The MRI scanner we will use differs from conventional scanners only in that the magnet strength is 3.0 T, rather than the more typical 1.5 T magnets used in routine clinical scanning. The patient will enter a large room where a powerful magnet is located. Patient will be instructed to remove all jewelry and other metal-containing objects. The patient will then be placed on a narrow table with plastic-encased metal coil close to the head. Next, the patient will be slid into a small tunnel approximately 6 feet long and 25 inches in diameter. The duration of the scan is approximately 30 minutes. A small mirror will be positioned above the patient's head so the other end of the scanner is visible. After the patient is positioned, the table will move the patient into the scanner itself. The patient will be in voice-communication with a technician or investigator via an intercom, and will have access to a squeeze bulb that generates a loud noise just in case the patient would like to be withdrawn at any point. Each patient will undergo two scanning sessions (pre and Day7 macimorelin or placebo). A computer display will be positioned at one end of the scanner and can be seen through the mirror above the patient's head. Patients will be asked to allow us to put one or two small, soft, rubber tubes, similar to straws, into his/her mouth. The tubes will be used to give patient small squirts of a flavored beverage while in the scanner. Patients will simply swallow, while keeping his or her head still. Patients will be given a CD with .gif images of their brain taken during the structural scan if it is their first time being scanned.
- Breakfast Test Meal: The breakfast test meal "calorie count" will be conducted to assess the effect of study drug on stimulating food intake. Precise source documents will be maintained recording every food item consumed during the breakfast test meal as well as the date, start time of food consumed and the quantity of food consumed. In order to ensure accuracy, the serving plate and every food item will be weighed in advance of serving. The remaining food items and plate will then be re-weighed and the weight subtracted from the original weight measured before the meal was served. It is essential that a surplus of food is offered so that availability of food does not limit caloric consumption. Calories for unit-dose foods (e.g., a carton of milk) will be derived from the product label; for other foods and beverages, calories will be calculated from a standardized software package. Appetite will be assessed by a VAS before and 1h after breakfast.
- Patients will be instructed to refrain from physical activity the day before testing on days 1 and 7 to avoid changes in REE that can be induced by exercise.

- All Information will be entered into Case Report Forms (CRF).

5.6 Day 1 Visit

- A complete history and physical exam will be performed. Special emphasis will be placed on evaluation for any signs of pedal edema, pleural effusions, and ascites. Body weight will be obtained on a calibrated scale dedicated for this study as indicated above. Patients will remove shoes, belts, wallets, keys, cell phones and any heavy clothing i.e. sweaters or sweatshirts. Underwear and a gown will be worn.
- A fasting blood sample will be obtained before dosing to measure CBC with Differential, comprehensive metabolic panel, glucose, IGF-1, GH, IGFBP-3, IL-6, CRP, and TNF-alpha and a UA (including hCG for females). A growth hormone level will be measured again 1 hour after dosing. An aliquot of the sample will be stored for up to 5 years after the study is completed to measure other inflammatory and anabolic markers.
- ECGs will be performed before dosing and again 1 hour after dosing.
- REE will be assessed by indirect calorimetry before dosing. Briefly, patients will rest in a supine position for at least 30 min before undergoing indirect calorimetry using a ventilated hood technique. This system provides measurements of VO_2 and VCO_2 , which have an error of less than 4% (39). This method is termed 'indirect' as the method of collection of gas is from a transparent hood placed over the head of the patient. One end of this hood is connected to the indirect calorimeter to measure CO_2 and O_2 content in the expired air. Air is drawn in from the other end of the tube, from which a portion is sampled to measure CO_2 and O_2 in the inspired air. Measurements were performed for at least 30 minutes. The measurements performed in the last 20 minutes will be averaged to calculate REE using the Weir equation (40). This method is currently considered one of the 'gold standard' methods to assess energy expenditure. Respiratory quotient (VCO_2/VO_2 ratio, RQ) will also be calculated as a measure of relative utilization of carbohydrates and fat.
- Body composition will be measured by BIA and DXA before dosing. BIA is a noninvasive method of estimating body composition based on the ability of tissues to conduct an electrical current. Based on this principle, lean tissue conducts electricity better than fat; therefore, the body composition analyzer/scale is able to calculate total body water, total body fat and total body lean mass. DXA scan uses a low amount of radiation to determine fat mass and bone mass and calculates fat-free mass (whole body and segmental).
- Functional performance will be assessed before dosing by: a) HGS and b) SCP. These tests have been shown to correlate with VO_2 max and are good tests of aerobic and functional capacity in cachectic states (41, 42). Briefly, HGS will be measured by a handheld dynamometer (Jamar Hydraulic Dynamometer, J.A. Preston Corp., Clifton, NJ) as described elsewhere (43). SCP, which allows measuring the

maximal anaerobic power of the involved muscles, will be performed as follows. At the moment of the first execution, 2–3 practice trials will be allowed so that the patients gained a good control of the performing technique. SCP consists in a modification of the test proposed by Margaria et al, (44), recently applied in elderly patients (45). In brief, patients will be invited to climb up ordinary stairs at the highest possible speed, according to their capabilities. The stairs will consist of 13 steps of 15.3 cm each, thus covering a total vertical distance of 1.99 m. An experimenter will measure the time employed to cover the test with a digital stopwatch. In line with Margaria et al. (44), assumptions, anaerobic power (in W) will be calculated by using the following formula: "body mass x 9.81 x vertical distance/time where body mass, vertical distance (i.e., 1.99 m) and time are expressed in kg, m and s, respectively, and 9.81 m/s² represents the acceleration of gravity. Physical activity will be monitored from Day 1 to Day 7 with the Actical Version 3.0 activity monitor (Respironics Inc., Murrysville, PA). The wrist-worn monitor will be provided on Day 1, along with verbal instructions for proper use, and worn for the entire 7-day study period until it is returned to study staff on the Day 7 visit.

- Previously validated questionnaires including the ECOG and Karnofsky scales will be administered. Patients will also complete the ASAS and FACIT-F questionnaires to assess changes in symptoms that play a role in performance such as fatigue.
- Food diary will be retrieved and information entered into the CRF. A new food diary will be given and patients asked to complete it 3 days before the next visit.
- Patients will be randomized as indicated above to placebo or macimorelin. All patients will receive the first dose before being discharged. Patients will be instructed to keep the drug in the refrigerator at 2-8° C and to take the drug on an empty stomach in the morning at least 1 h before breakfast, because it was previously demonstrated that the administration of macimorelin with food significantly reduced its GH secretagogue efficiency and bioavailability. The research Pharmacy will provide each patient with 5 syringes (days 2 through 6) with either Powerade® alone (placebo) or macimorelin diluted in the same volume of Powerade®. Patients will be also provided with a bag and asked to return the empty syringes for drug accountability.
- Patients will be asked to refrain from physical activity the day before the next visit to avoid changes in REE that can be induced by exercise. Patients will be asked not to take the dose of study drug the day of the Day 7 visit.
- All Information will be entered into CRFs.

5.7 Day 7 Visit

- The Actical activity monitor will be returned to study staff at the beginning of this visit.

- A complete history and physical exam will be performed as indicated above. Special emphasis will be placed on evaluation for AEs and any signs of pedal edema, pleural effusions, and ascites. Body weight will be obtained on calibrated scale dedicated for this study as indicated above. Patients will remove shoes, belts, wallets, keys, cell phones and any heavy clothing i.e. sweaters or sweatshirts. Underwear and a gown will be worn.
- A fasting blood sample will be obtained before dosing to measure CBC with Differential, comprehensive metabolic panel, glucose, IGF-1, GH, IGFBP-3, IL-6, CRP, and TNF-alpha and UA (including hCG for females). A growth hormone level will be measured again 1 hour after dosing. An aliquot of the sample will be stored for up to 5 years after the study is completed to measure other inflammatory and anabolic markers.
- ECGs will be performed before dosing and again 1 hour after dosing.
- REE, BIA, DXA, HGS, and SCP will be assessed as indicated above.
- Questionnaires including the ECOG and Karnofsky scales will be administered. Patients will also complete the ASAS and FACIT-F questionnaires to assess changes in symptoms that play a role in performance such as fatigue. Patients will receive at this time the study drug dose.
- A new MRI session (equal to the one on Screening Visit) will be administered approximately 45 minutes after dosing but before the test meal.
- Breakfast Test Meal will be provided 1.5 hours after dosing with the same items and amount provided at the screening visit. Appetite will be assessed by a VAS before and 1h after breakfast. Food diary will also be retrieved at this visit.
- Blood samples for GH measurements will be obtained 1h after dosing.
- Drug accountability will be assessed by counting the number of empty syringes that the patient returned.
- All Information will be entered into CRFs.

5.8 Post-Study Visit

- An H&P will be repeated by the PI with special emphasis on AEs. A fasting blood sample will be collected as previously described for measurement of safety labs including CBC with Diff, comprehensive metabolic panel, hCG (for females), UA. An ECG will be performed.

5.9 Recruitment Methods

Eight total participants who complete the entire protocol are needed. Participants will be recruited from the Oncology clinic through our collaborator [name] and his clinical staff as follows:

- Study staff accesses medical records to identify potential participants from oncology clinic
- Study staff reviews records to ascertain initial inclusion/exclusion criteria
- Study staff sends list of potential participants to clinical staff
- Clinical staff brings up potential research study to patient at clinical visit and asks if they're interested in learning more
- Study staff then speaks with patients to provide more information
- If patient is interested they sign a consent form
- Screening/baseline visit occurs

5.10 Informed Consent Procedure

- The PI and his staff will consent patients. Patients will be identified through analysis of electronic medical records at the VAPSHCS by our collaborator, the Oncologists, and the research staff. Patients will be approached by study staff at their cancer clinic after clinical staff brings up potential research study to patient at clinical visit and asks if they're interested in learning more. Patients are offered the informed consent form for consideration of volunteering for the study. Staff will explain the study to patients, providing a signed copy of the consent for their records. Patients will be assured of the voluntary nature of the trial and a member of the research staff will be available to answer all questions regarding the study. We will emphasize that their decision to participate in the clinical trial will not affect their treatment.
- A waiver of consent is requested for identification/screening. The use or disclosure of protected health information involves no more than minimal risk to the individuals and the waiver will not adversely affect the privacy rights and the welfare of the individuals. The risk is minimal because: 1) only trained personnel will have access to this information, 2) information will be accessed only from our research office at the VA and kept in a locked cabinet behind locked doors or in password-protected computers and 3) only information absolutely required for research will be obtained and recorded (full medical history, name, date of birth, and last 4 numbers of the SSN).The research could not practicably be conducted without this waiver and could not practicably be conducted without access to and use of the protected health information because accessing potential patients' medical records and their last 4 digits of their SSN and name is required to approach them to explain the proposed research and consent them.
- An adequate plan exists in order to protect health information (PHI) identifiers from improper use and disclosure to minimize the risk of loss of confidentiality as recommended by VA guidelines. Adequate written assurances exist in order to ensure

that the PHI will not be reused or disclosed to (shared with) any other person or entity, except as required by law, for authorized oversight of the research study, or for other research for which the use or disclosure of the PHI would be permitted under the Privacy Rule to minimize the risk of loss of confidentiality as recommended by VA guidelines.

- Study personnel will be trained regarding human subjects' protections requirements and how to obtain and document informed consent as it is required by local and Federal VA guidelines. All study documents containing PHI will be kept in a locked cabinet inside a locked room. No data containing PHI will be accessible outside the study site. The room is kept locked with the door shut. No patient data is left out of the cabinets. Confidential information will be stored on servers managed and maintained by the VA-IT program. All computers are password protected.
- Sub-investigators will be provided the participant study number and de-identified (all 18 HIPAA identifiers will be removed prior to sending data outside the VA) study data for analysis. No sensitive information will be share and the data will be transferred electronically via secure email. No social security numbers will be requested from patients or potential patients via phone.
- The PI, VA collaborators, research staff, and VA research compliance monitors will have access to identifiable information. People who ensure quality from the institutions where the research is being done, federal and other regulatory agencies will have access to all of the research data. No else will have access to identifiable research data. An Accounting of Disclosure (AOD) will be created and maintained for any disclosure of individually identifiable information (III) outside the VA. The manual spreadsheet will include the date of the disclosure, nature or description of the III disclosed, purpose of each disclosure and the name and address of person or agency to which the disclosure was made.

5.11 Inclusion/Exclusion Criteria

5.11.1 Inclusion Criteria

1. Patients ≥ 18 years of age with histological diagnosis of active solid or hematological malignancies
2. ECOG performance status of 0-2,
3. Presence of cancer-related cachexia defined as an involuntary weight loss of at least 5% over the previous 6 months, 10% over the previous 12 months or 2% over the previous 6 months with a BMI < 20, and
4. Provide written informed consent prior to screening.

5.11.2 Exclusion Criteria

1. Obesity (body weight >140 Kg);
2. Recent active excessive alcohol or illicit drug use;
3. Severe depression as determined by the investigator;
4. Other causes of cachexia such as: Liver disease (AST or ALT > 3x normal levels); renal failure (creatinine > 1.5 mg/dL), untreated thyroid disease, class III-IV CHF, AIDS, severe COPD requiring use of home O₂;
5. Inability to increase food intake (e.g., esophageal obstruction, intractable nausea and vomiting);
6. Any condition that would prevent the patient from performing the research procedures (e.g., unstable coronary artery disease);
7. Use of growth hormone, megestrol, Marinol, or any other anabolic agents, appetite stimulants, tube feeding, or parenteral nutrition during the 1 month prior to entering the study;
8. Systemic corticosteroids administration for > 6 days a month (i.e.daily continuous schedule).
9. Recent administration (less than 1 week) of highly emetogenic chemotherapy (Hesketh scale class 4-5); patients may otherwise be undergoing chemotherapy.
10. Being female and pregnant, breast-feeding or of childbearing potential. (Note: Lack of childbearing potential for female patients is satisfied by: a) being post-menopausal; b) being surgically sterile; c) practicing contraception with an oral contraceptive, intra-uterine device, diaphragm, or condom with spermicide for the duration of the study; or d) being sexually inactive. Confirmation that the patient is not pregnant will be established by a negative urine hCG pregnancy test at the time of enrollment.
11. Co-administration of drugs that prolong QT interval (Appendix II), CYP3A4 inducers (Appendix III), QTc equal to greater than 450ms at screening or other investigational agents (a wash-out period of five times the half-life of drugs that prolong QT will be allowed with approval of prescriber).
12. Conditions that would preclude from successfully scanning patients in MRI: a. Claustrophobia (this would make lying in the scanner very uncomfortable); b. having a pacemaker, aneurysm clips, neurostimulators, cochlear implants, metal in eyes, steel worker, or other implants; c. History of Seizures; d. History of head injuries resulting in loss of consciousness > 10 minutes.

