	
previous 6 months, and
 
4. Provide written informed consent prior to screening.
 
Exclusion:
 
 1. Obesity (body weight >140 Kg); 2. Recent active excessive alcohol or illicit drug use; 3. Severe depression as determined by the investigator; 4. Other causes of cachexia such as: Liver disease (AST or ALT > 3x normal levels); renal failure (creatinine >1.5 mg/dL), untreated thyroid disease, class III-IV CHF, AIDS, severe COPD requiring home O₂; 5. Inability to increase food intake (e.g., esophageal obstruction, intractable nausea and vomiting); 6. Any condition that would prevent the patient from performing the research procedures (e.g. unstable coronary artery disease); 7. Use of growth hormone, megestrol, Marinol, or any other anabolic agents, appetite stimulants, tube feeding, or parenteral nutrition during the 1 month prior to entering the study. 8. Systemic corticosteroids administration for > 6 days a month (i.e. daily continuous schedule). 9. Recent administration (less than 1 week) of highly emetogenic chemotherapy (Hesketh scale class 4-5); patients may otherwise be undergoing chemotherapy. 10. Being female and pregnant, breast-feeding or of childbearing potential. (Note: Lack of childbearing potential for female patients is satisfied by: a) being post-menopausal; b) being surgically sterile; c) practicing contraception with an oral contraceptive, intra-uterine device, diaphragm, or condom with spermicide for the duration of the study; or d) being sexually inactive. Confirmation that the patient is not pregnant will be established by a negative urine hCG pregnancy test at the time of enrollment. 11. Co-administration of drugs that prolong QT interval (Appendix II), CYP3A4 inducers (Appendix III), QTc equal to greater than 450ms at screening or other investigational agents (a wash-out period of five times the half-life of drugs that prolong QT will be allowed with approval of prescriber). 12. Conditions that would preclude from successfully scanning patients in MRI: 
 a. Claustrophobia (this would make lying in the scanner very uncomfortable); b. having a pacemaker, aneurysm clips, neurostimulators, cochlear implants, metal in eyes, steel worker, or other implants; c. History of Seizures, d. History of head injuries resulting in loss of consciousness > 10 minutes.

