Macimorelin is metabolized mainly by CYP3A4 but has no CYP3A4 inhibitory activity. Therefore, macimorelin is not expected to affect the plasma concentrations of other drugs metabolized by CYP3A4. Potent inhibitors or inducers of CYP3A4 may affect the pharmacokinetic profile of macimorelin. Co-administration of potent CYP3A4 inhibitors or inducers should be avoided. Please see the Investigators Brochure for the complete background on this drug.

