APPENDIX II: DRUGS THAT PROLONG THE QT INTERVAL

<http://www.azcert.org/advisory-committee.cfm>

Generic Name/ Name Class/Clinical Use Comments

Clomipramine Anafrani® Tricyclic Antidepressant / depression
Trimethoprim
Sulfa Bactrim® Antibiotic / bacterial infection
Diphenhydramine Benadryl® Antihistamine / Allergic rhinitis, insomnia
Citalopram Celexa® Anti-depressant / depression
Ciprofloxacin Cipro® Antibiotic / bacterial infection
Trazodone Desyre® Anti-depressant / Depression,insomnia
Fluconazole Diflucan® Anti-fungal / fungal infection
Amitriptyline Elavil® Tricyclic Antidepressant / depression
Ketoconazole Nizoral® Anti-fungal / fungal infection
Imipramine Norfranil® Tricyclic Antidepressant / depression
Ritonavir Norvir® Protease inhibitor! HIV
Diphenhydramine Nytol® Antihistamine / Allergic rhinitis, insomnia
Nortriptyline Pamelor® Tricyclic Antidepressant / depression
Paroxetine Paxil® Anti-depressant / depression
Desipramine Pertofrane® Tricyclic Antidepressant / depression
Fluoxetine Prozac® Anti-depressant / depression
Galantamine Reminyl® Cholinesterase inhibitor / Dementia, Alzheimer's
Fluoxetine Sarafem® Anti-depressant / depression
Doxepin Sinequan® Tricyclic Antidepressant / depression
Itraconazole Sporanox® Anti-fungal / fungal infection
Trimethoprim

Sulfa Sulfa® Antibiotic / bacterial infection

Trimipramine Surmontil® Tricyclic Antidepressant / depression
muscarinic receptor

Solifenacin VESicare® antagonist | treatment of overactive bladder

Protriptyline Vivactil® Tricyclic Antidepressant / depression

Sertraline Zoloft® Anti-depressant / depression

Escitalopram Cipralex® Anti-depressant | Major depression | Anxiety disorders

Dolasetron Anzemet® Anti-nausea / nausea, vomiting

Moxifloxacin Avelox® Antibiotic / bacterial infection

Nicardipine Cardene® Anti-hypertensive / high blood pressure

Fosphenytoin Cerebyx® Anti-convulsant | seizure

Clozapine Clozaril® Anti-psychotic /schizophrenia

Perflutren lipid Definity® Imaging contrast agent | microspheres Echocardiography

Isradipine Dynacirc® Anti-hypertensive / high blood pressure

Venlafaxine Effexor® Anti-depressant | depression

Lithium Eskalith® Anti-mania / bipolar disorder

Gemifloxacin Factive® Antibiotic | bacterial infection

Felbamate Felbatol® Anti-convulsant | seizure

Ofloxacin Floxin® Antibiotic | bacterial infection

Foscarnet Foscavir® Anti-viral / HIV infection

Ziprasidone Geodon® Anti-psychotic/schizophrenia

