APPENDIX III: DRUGS THAT INDUCE CYP3A4

CYP3A4 inducers which are considered to be clinically relevant are: carbamazepine, phenobarbital, phenytoin, pioglitazone, rifabutin, rifampin, St. John's wort, troglitazone Avasimibe, Bosentan, efavirenz, etravirine, modafinil, nafcillin, Amprenavir, aprepitant, armodafinil, echinacea, pioglitazone, prednisone, rufinamide

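### Section 2.7 advises against potent CYP3A4 inhibitors as well as inducers, but exclusion criterion 11 and Appendix III cover inducers only

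*Combined protocol and SAP*

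**What the plan says.** Section 2.7 makes three linked statements about metabolism. First, "Macimorelin is metabolized mainly by CYP3A4 but has no CYP3A4 inhibitory activity". Second, "Potent inhibitors or inducers of CYP3A4 may affect the pharmacokinetic profile of macimorelin". Third, as the resulting advice, "Co-administration of potent CYP3A4 inhibitors or inducers should be avoided". It then refers the reader to the Investigators Brochure for the full background.

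The eligibility rule is exclusion 11 in Section 5.11.2: "Co-administration of drugs that prolong QT interval (Appendix II), CYP3A4 inducers (Appendix III), QTc equal to greater than 450ms at screening", followed by other investigational agents and a washout allowance for QT-prolonging drugs. The synopsis carries the same wording. The two supporting lists are headed "APPENDIX II: DRUGS THAT PROLONG THE QT INTERVAL" and "APPENDIX III: DRUGS THAT INDUCE CYP3A4".

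On the minor point, the synopsis requires at least 5% weight loss over six months. Section 5.11.1 accepts that, or 10% over twelve months, or 2% over six months with a BMI below 20.

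**The concern.** Section 2.7 treats inhibitors and inducers alike. Inducers then receive an exclusion and an appendix, and inhibitors receive neither. Nothing in the protocol explains the difference.

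This matters because patients are selected on the criteria and not on background text. Section 5.9 states "Study staff reviews records to ascertain initial inclusion/exclusion criteria", and Section 5.5 repeats the review of criteria after consent. Neither step would stop a patient on an inhibitor that Appendix II does not list.

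For a drug cleared mainly by CYP3A4, the expected direction of an inhibitor's effect is higher exposure. That is an inference; Section 2.7 says only that the pharmacokinetic profile may change. The same section reports one serious event judged likely due to macimorelin, a possible rhythm abnormality on an ECG 60 minutes after dosing that led to hospital admission. Patients here may be receiving chemotherapy and take the doses on days 2 to 6 at home.

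**Working it through.** The plan states no figure on this point, so the check compares texts and makes a few counts.

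**1. Classes advised against and classes excluded**

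| Place | Potent CYP3A4 inhibitors | CYP3A4 inducers |
|---|---|---|
| Section 2.7 (advice) | avoid | avoid |
| Synopsis, exclusion 11 | not named | excluded |
| Section 5.11.2, exclusion 11 | not named | excluded |
| Appendix III | none listed | listed |

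One of the two classes in Section 2.7 reaches the criteria.

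**2. Content of Appendix III.** Carbamazepine to troglitazone gives 8 entries, avasimibe to nafcillin 6, and amprenavir to rufinamide 7: 8 + 6 + 7 = 21. Pioglitazone appears twice, so 21 − 1 = 20 distinct drugs. All are presented as inducers and none is labelled an inhibitor.

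**3. Any other restriction.** CYP3A4 inhibitors are not mentioned as a class outside Section 2.7. The contents list shows no section on concomitant medication. Exclusion 7 covers growth hormone, appetite stimulants, other anabolic agents and nutritional support. Exclusion 8 covers corticosteroids. Neither supplies the missing rule.

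**4. Incidental cover from Appendix II.** The QT list bars ketoconazole, itraconazole, ritonavir, atazanavir, telithromycin and clarithromycin, among others. The documents do not classify any of these as CYP3A4 inhibitors. If some of them are potent inhibitors, the gap is narrower, but a list built on QT effect cannot be relied on to cover a class defined by enzyme inhibition.

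**5. Upper bound on patients.** About 8 patients are to be randomized 3:1, so 8 × 3/4 = 6 are planned on macimorelin, in line with the abstract. Only these can have altered macimorelin exposure. One such patient would be 1/6, or about 17%, of the arm. The expected number cannot be derived, because the documents give no frequency of inhibitor use.

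**6. Cachexia definition (minor).** A patient with 10% loss over twelve months but under 5% in the last six passes Section 5.11.1 and fails the synopsis. So does a patient with 2% to under 5% loss over six months and a BMI below 20. Only the synopsis inclusion list names pre-illness weight as the reference. The abstract gives more than 5% with no period, as background.

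**The case against.** The strongest reply is that the practical gap is small and undemonstrated. Section 2.7 gives advice in a background section, no specific admissible inhibitor is identified, and the documents do not say which inhibitors are potent. Appendix II already bars a long list of drugs. A screening QTc of 450 ms or more excludes the patient, and ECGs are taken before and one hour after dosing on days 1 and 7. Section 2.7 also reports that doses up to four times the study dose were well tolerated in a trial with 28 healthy volunteers, and that most toxicity findings arose at about 1000 times the anticipated human exposure. The Investigators Brochure may give further guidance.

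Much of this stands as a limit on the risk. It does not remove the inconsistency. The screening QTc is measured before any study drug is given, and the later ECGs detect an effect but do not prevent the exposure. Tolerability in healthy volunteers is not interaction data in cancer patients on other medication, and it did not lead the authors to withdraw the advice. The brochure is not among the documents, and referring to it does not create an eligibility rule.

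It is also fair to say that the cachexia wording is a separate matter. It is noted here only because it is another mismatch in eligibility, and it carries no weight in the main conclusion.

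**Conclusion.** The concern holds. The criteria put into effect one of the two CYP3A4 restrictions that the protocol gives for its own drug, and following them exactly can enrol a patient whom Section 2.7 says should not be co-medicated. This should be corrected, but it is not evidence of harm.

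At most the six planned macimorelin patients are exposed to the problem. The true number and the change in drug exposure are unknown from the documents. The conclusion rests on the text alone, with one assumption: that at least one potent CYP3A4 inhibitor is absent from Appendix II and not caught by another criterion. If there were none, the defect would be one of wording only, and the same correction would still be sensible.

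The cachexia mismatch is real and minor.

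**What to change.** In exclusion 11, in both the synopsis and Section 5.11.2, name potent CYP3A4 inhibitors alongside CYP3A4 inducers, with the reference to Appendix III. Add a list of potent inhibitors to Appendix III and retitle it to cover both classes. The documents contain no such list, so the sponsor must supply one and give its source. The washout allowance in exclusion 11 applies only to QT-prolonging drugs, so it would help to say whether one is also allowed for inhibitors.

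For the minor point, the sponsor should confirm which cachexia definition governs, presumably that of Section 5.11.1, and use it in the synopsis Population row and inclusion list. The sponsor should also decide whether pre-illness weight is the reference, and either align the abstract's figure or mark it as a general description.

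The cost is one phrase in two exclusion lists, one added list and a new appendix title, plus two synopsis entries and one abstract phrase for the minor point. The downside is a slightly smaller eligible pool.
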